9.7.1.8.2 ADVERSE EVENTS

The AE verbatim descriptions (investigator terms from the eCRF) will be classified into standardized medical terminology using the Medical Dictionary for Regulatory Activities (MedDRA). Adverse events will be coded to the MedDRA (Version 17.0 or higher) lower level term closest to the verbatim term. The linked MedDRA preferred term and primary system organ class (SOC) are also captured in the database.

A TEAE is defined as an AE that emerges during treatment, having been absent at pretreatment (Baseline) or

- Reemerges during treatment, having been present at pretreatment (Baseline) but stopped before treatment, or
- Worsens in severity during treatment relative to the pretreatment state, when the AE is continuous.

Only those AEs that are treatment-emergent will be included in summary tables. All AEs, treatment-emergent or otherwise, will be presented in subject data listings.

The TEAEs will be summarized by treatment group on the Safety Analysis Set. The incidence of TEAEs will be reported as the number (percentage) of subjects with TEAEs by SOC and preferred term. A subject will be counted only once within an SOC and preferred term, even if the subject experienced more than 1 TEAE within a specific SOC and preferred term. The number (percentage) of subjects with TEAEs will also be summarized by maximum severity (mild, moderate, or severe). The number (percentage) of subjects with

TEAEs will also be summarized by relationship to study drug (Yes [related] and No [not related]).

The number (percentage) of subjects with treatment-related TEAEs will be summarized by SOC and preferred term. Treatment-related TEAEs include those events considered by the investigator to be related to study drug. The number (percentage) of subjects with treatment-related TEAEs will also be summarized by maximum severity (mild, moderate, or severe).

Adverse events will be summarized by the following subgroups: *ApoE4* status (positive or negative), prior treatment with AChEIs or memantine (no or yes), and clinical population (MCI/Prodromal or mild to moderate AD). (revised per Amendment 01)

The number (percentage) of subjects with TEAEs leading to death will be summarized by MedDRA SOC and preferred term for each treatment group. A subject data listing of all AEs leading to death will be provided.

The number (percentage) of subjects with treatment-emergent SAEs will be summarized by MedDRA SOC and preferred term for each treatment group. A subject data listing of all SAEs will be provided.

The number (percentage) of subjects with TEAEs leading to discontinuation from study drug will be summarized by MedDRA SOC and preferred term for each treatment group. A subject data listing of all AEs leading to discontinuation from study drug will be provided.

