reductions in CD4 (T helper cells), CD8 (cytotoxic T cells), and CD19 (B cells) counts at Day 8. These reductions were more clearly evident by Day 15, consistent with a treatment by time interaction in the statistical analysis. There was evidence that the lower doses of 50 to 100 mg also caused some reduction in CD4 lymphocyte counts by Day 15. Doses above 100 mg appeared to be associated with greater reductions in CD4 and CD8 lymphocyte counts, which occurred earlier in the treatment period compared with the effects of 25 to 100 mg doses. These effects on lymphocyte counts gradually resolved from Day 20 to Day 35, which were 6 and 21 days, respectively, after administration of the last dose of E2609 on Day 14. Reductions in CD4 and CD8 lymphocyte counts at doses of 200 and 400 mg to a level close to or less than the lower limit of normal (LLN) could be associated with increased risk of developing relapse of orolabial herpes or other infections.

In Study 003, a drug-drug interaction study, PK results showed that itraconazole (a potent inhibitor of cytochrome P450 [CYP3A4] and carboxyesterase-2 [CES2]) increased by approximately 70% the area under the concentration \times time curve (AUC) of E2609. Consequently, strong inhibitors of CYP3A4 will be prohibited in this study.

Rifampin (a potent CYP3A4 inducer) caused a mild decrease (by approximately 20%) of the AUC of E2609. Therefore, no restrictions are required for the use of concomitant medications which are known to be inducers of CYP450 enzymes. Donepezil (a moderate CES2 inhibitor) caused a mild increase (by approximately 20%) of the AUC of E2609 when coadministered with E2609 but not when dosed at least 2 hours apart from E2609. E2609 (which inhibits the P-glycoprotein 1 transporter) did not affect the PK properties of digoxin. Nonclinical studies also indicated that other CYP pathways apart from CYP3A4 would not be major pathways of metabolism of E2609. Therefore, on the basis of drug interaction considerations, the only restriction of concomitant medications is that for strong inhibitors of CYP3A4.

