9.1.2 Randomization Phase

Subjects who complete the Baseline Visit assessments, and are eligible based on the inclusion and exclusion criteria (see [Section 9.3.1](#) and [Section 9.3.2](#)), will begin the Randomization Phase within 7 to 10 days following completion of the Baseline Visit assessments.

The Randomization Phase will consist of a Treatment Period of 78 weeks duration and a Follow-Up Period of 12 weeks after the last dose of study drug.

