9.5.1.5.1 ADVERSE EVENTS AND EVENTS ASSOCIATED WITH SPECIAL SITUATIONS

An AE is any untoward medical occurrence in a subject or clinical investigation subject administered an investigational product. An AE does not necessarily have a causal relationship with the medicinal product. For this study, the study drug is E2609.

The criteria for identifying AEs in this study are:

- Any unfavorable and unintended sign (including an abnormal laboratory finding), symptom, or disease temporally associated with the use of an investigational product, whether or not considered related to the investigational product (Note: It is not necessary to report every sign or symptom as a separate AE if the overall disease [diagnosis] is being reported as an AE.)
- Any new disease or exacerbation of an existing disease
- Any deterioration in nonprotocol-required measurements of a laboratory value or other clinical test (eg, ECG or x-ray) that results in symptoms, a change in treatment, or discontinuation of study drug
- Recurrence of an intermittent medical condition (eg, headache) not present pretreatment (Baseline)
- An abnormal laboratory test result should be considered an AE if the identified laboratory abnormality leads to any type of intervention, discontinuation of study drug, or withholding of study drug, whether prescribed in the protocol or not

All AEs observed during the study will be reported on the eCRF. All AEs, regardless of relationship to study drug or procedure, should be collected beginning from the time the subject signs the study ICF through the last visit (Visit 20, as shown in [Table 7](#)). For subjects who discontinue early from study drug but undertake further efficacy assessments, AEs will only be collected for 3 months after the last dose of study drug, ie, through to the second follow-up visit (Visit 20). Subjects who fail screening primarily due to AE(s) must have the AE(s) leading to screen failure reported on the Screening Disposition eCRF. SAEs will be collected for 3 months after the last dose of study drug, ie, through to the second follow-up visit (Visit 20). For subjects who discontinue early from study drug but continue with further efficacy assessments, SAEs will be solicited only for 3 months after the last dose of study drug, i.e. up to the 2nd follow up visit (Visit 20). However, any SAEs volunteered by subjects after this time point must be reported according to standard procedures.

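### Adverse events that first appear in the 12 weeks after the last dose are collected and listed, but the TEAE rule keeps them out of every by-arm AE summary table

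*Protocol*

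**What the plan says.** Protocol Section 9.7.1.8.2, in the version carrying Amendment 01, begins its definition: "A TEAE is defined as an AE that emerges during treatment, having been absent at pretreatment (Baseline". The other two limbs, return of an event that had stopped before treatment and increase in severity, are bounded by the same period. No number of days after the last dose is given.

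The section then restricts the tables: "Only those AEs that are treatment-emergent will be included in summary tables". Everything else goes to listings: "All AEs, treatment-emergent or otherwise, will be presented in subject data listings". The tables of serious and fatal events carry the same restriction: "The number (percentage) of subjects with treatment-emergent SAEs will be summarized by MedDRA SOC and preferred term for each treatment group", and "The number (percentage) of subjects with TEAEs leading to death will be summarized by MedDRA SOC and preferred term for each treatment group".

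Section 9.1.2 keeps treatment and follow-up apart, as "a Treatment Period of 78 weeks duration and a Follow-Up Period of 12 weeks after the last dose of study drug". Section 9.5.1.5.1 collects AEs from consent through Visit 20. For subjects who stop drug early but return for efficacy visits, "AEs will only be collected for 3 months after the last dose of study drug", which that section equates with Visit 20.

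On carry-over, Section 7.1 reports from the 14-day multiple-dose study: "These effects on lymphocyte counts gradually resolved from Day 20 to Day 35, which were 6 and 21 days, respectively", counted from the final dose on Day 14.

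**The concern.** The protocol goes to some trouble to gather off-drug safety data. Section 9.2.6 lists the two off-treatment visits among its risk-mitigation measures. Section 9.3.3 follows subjects taken off drug with an infection for at least 12 weeks. Section 9.7.3 calls for 3 months of safety monitoring if the study stops for futility. The tabulation rule then leaves new events from that period without a count by arm.

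The first of the two safety aims named in Section 8.1's second primary objective is safety including immunological and hematological parameters. If lymphocyte effects outlast dosing by up to three weeks, an infection that starts in those weeks is the kind of event for which a comparison of arms is wanted. Under the rule as written, the reader of the study report would have to assemble that comparison from listings.

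**Working it through.** The point rests on definitions, so the check is to trace an event through the rules and then measure the untabulated window.

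1. **The plan's carry-over figure.** Section 7.1 gives the last dose on Day 14 and resolution from Day 20 to Day 35. 20 − 14 = 6 days and 35 − 14 = 21 days. The stated 6 and 21 days are reproduced.

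2. **Length of the off-drug window.** Table 7 puts Visit 18 at Day 547, Visit 19 at Day 575 and Visit 20 at Day 631. 631 − 547 = 84 days = 12 weeks. 575 − 547 = 28 days, so Visit 19 falls at last dose + 28 days for a completer. The 21-day recovery lies wholly inside the 84 days.

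3. **Tracing an event.** Take an infection that starts 10 days after the last dose.
   - Section 9.5.1.5.1: it is collected, because Visit 20 has not passed.
   - Section 9.7.1.8.2, definition: it did not emerge, return or worsen while on treatment, so it is not a TEAE.
   - Section 9.7.1.8.2, tables: it is in no AE, SAE or death summary, only in a listing.
   - The same holds for an onset between the last dose and the Early Discontinuation Visit, which may be up to 7 days later (Section 9.1.2.2).
   - By contrast, an infection that starts on drug and continues afterwards, or proves fatal afterwards, is a TEAE and is counted.

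4. **Contrast with the laboratory rule.** Section 9.7.1.8.3 counts any qualifying postbaseline value as a treatment-emergent markedly abnormal value (Grade 2 or higher; Grade 3 or higher for phosphate), with no stop at the last dose. It also summarizes laboratory values, lymphocyte subsets included, at each postbaseline visit. An off-drug fall in counts can therefore be tabulated while an off-drug infection cannot.

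5. **Size of the window.** Share of post-first-dose AE collection time that falls after the last dose = 12 / (weeks on drug + 12). Only the 78-week row is the planned course; the other stopping times are assumed, to show the range.

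| Weeks on drug | Calculation | Share of collection time |
|---|---|---|
| 78 (completer) | 12/90 | 13.3% |
| 52 | 12/64 | 18.8% |
| 26 | 12/38 | 31.6% |
| 12 | 12/24 | 50% |
| 8 | 12/20 | 60% |
| 4 | 12/16 | 75% |

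**The case against.** **The cut-off is a matter for the SAP.** Section 9.7.1 defers further analytical detail to the SAP, and Section 9.7.1.8.3 shows that the protocol does not always use the term treatment-emergent strictly. A SAP could add a lag. But Section 9.7.1.8.2 does not leave the matter open: it fixes the period and says that only such events are tabulated, and Section 9.1.2.3 calls the follow-up visits posttreatment. Section 9.7.1.8 speaks loosely of summarizing the incidence of AEs, but the specific rule governs.

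**The text may have been superseded.** Appendix 2, Listing 2 also appears in a form revised under Amendment 02, and the statistical section of that version is not shown. This stands as a limit on the point.

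**The carry-over evidence is thin.** It comes from 14 days of dosing. Section 7.1 ties possible infection risk to low counts at 200 and 400 mg, whereas the top dose here is 50 mg. Section 9.4.4 reports a 3.1% CD4 decrease at 100 mg and no infection or drug rash on drug at 100 mg or below. Section 7.1 does report some CD4 reduction at 50 to 100 mg. What stands is that the evidence supports about three weeks of carry-over, not twelve.

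**Nothing is hidden.** This stands. All AEs are listed, with dedicated listings of all fatal AEs and all SAEs. Lymphocyte counts are summarized by visit, and the DSMB sees all safety data unblinded (Section 9.1).

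**On-treatment incidence is a legitimate quantity, and the event that triggers stopping usually starts on drug.** Both stand. A subject stopped under Section 9.3.3 for infection or rash will usually already be counted for that event; only new off-drug terms are lost. This favors a separate off-drug table over merging all 12 weeks into the TEAE definition.

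**Conclusion.** The point holds as a stated rule that works against the protocol's own safety follow-up. AEs with first onset in the 84 days after the last dose are collected and listed but appear in no by-arm AE, SAE or death summary. The window is 13% of post-first-dose AE collection time for a completer and a larger share for early discontinuers. The primary efficacy analysis is unaffected.

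A reader might infer three stronger things, none of which the documents support:

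- *That 13% or 60% of events go missing.* These are shares of calendar time. No off-drug event rate is given, and the week-8 stop behind the 60% is hypothetical.
- *That incidence is understated more in some arms than in others.* That would need both more early stopping and more new off-drug events in those arms; neither is shown.
- *That the drug's immune effect lasts the full 12 weeks, or that serious off-drug events go unreported.* The reported recovery was complete by 21 days, and serious and fatal events are all listed.

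The conclusion assumes that treatment ends at the last dose, which is how Sections 9.1.2 and 9.1.2.3 separate the periods. It also assumes that neither the Amendment 02 statistical section nor the SAP has changed the rule.

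**What to change.** Replace the open-ended period in Section 9.7.1.8.2 with dates: a TEAE is an AE that starts, returns or worsens from the first dose through a stated number of days after the last dose, judged by onset date. The number should cover the documented 21-day carry-over. Last dose + 28 days does so and matches the nominal timing of Visit 19.

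Add a separate incidence table by arm for AEs, SAEs and deaths with onset after that window through Visit 20. Show in it how many subjects in each arm were still under AE collection, since follow-up will differ. Settle this before treatment codes are released for the final analysis, so that the window is not chosen after an off-drug infection or death has been seen.

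The cost is one sentence and one extra set of tables from data already being collected. The small downside is that some late events unrelated to drug will be counted; keeping them in a separate table limits the effect on the TEAE figures.

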9.7.1.8.3 LABORATORY VALUES

Laboratory results will be summarized using International System of Units, as appropriate. For all quantitative parameters listed in [Section 9.5.1.5.3](#), the actual value and the change from baseline to each postbaseline visit and to the end of treatment (defined as the last on-treatment value) will be summarized by visit and treatment group using descriptive statistics. Qualitative parameters listed in [Section 9.5.1.5.3](#) will be summarized using frequencies (number and percentage of subjects), and changes from baseline to each postbaseline visit and to end of treatment will be reported using shift tables. Percentages will be based on the number of subjects with both nonmissing baseline and relevant postbaseline results.

Laboratory test results will be assigned a low/normal/high (LNH) classification according to whether the value was below (L), within (N), or above (H) the laboratory parameter's reference range. Within-treatment comparisons for each laboratory parameter will be based on 3-by-3 tables (shift tables) that compare the baseline LNH classification to the LNH classification at each postbaseline visit and at the end of treatment. Similar shift tables will also compare the baseline LNH classification to the LNH classification for the highest and lowest value during the treatment period.

[Appendix 1](#) (Sponsor's Grading for Laboratory Values) presents the criteria that will be used to identify subjects with treatment-emergent markedly abnormal laboratory values

(TEMAVs). Except for phosphate, a TEMAV is defined as a postbaseline value with an increase from baseline to a Grade of 2 or higher. For phosphate, a TEMAV was defined as a postbaseline value with an increase from baseline to a Grade of 3 or higher. When displaying the incidence of TEMAVs, each subject may be counted once in the laboratory parameter high and in the laboratory parameter low categories, as applicable.

Lymphocyte subsets (ie, CD4 [T helper cells], CD8 [cytotoxic T cells], CD19 [B cells], CD16/CD56 [natural killer cells] and CD14 [macrophages]) and regulatory T cells will be summarized in the same manner as other laboratory parameters. Mean lymphocyte subsets and the mean change from baseline in lymphocyte subsets will also be displayed graphically over time by dose.

Serum IgG, IgM, and IgA will be measured and summarized in the same manner as other laboratory parameters.

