Subjects who discontinue taking study drug prematurely for any reason will undergo an Early Discontinuation (ED) Visit within 7 days of their last dose of study drug. Follow-Up Visits will also be scheduled 4 and 12 weeks after the last dose of study drug. Subjects who discontinue study drug prematurely will also be scheduled to return to the study site for each scheduled visit when clinical efficacy assessments are to be conducted (ie, at Visits 11, 14, 15, 16, 17, and 18) if these visits have not already been performed. At these visits, only the clinical efficacy assessments (MMSE, CDR, ADAS-cog₁₄, FAQ, CBB and ISLT) will be conducted. Subjects who discontinue early from study drug are considered on study as long as they return for their regularly scheduled clinical efficacy visits as outlined above.

Follow-Up

All subjects, regardless of whether they complete all 18 months of treatment or discontinue study drug prematurely, will complete 2 posttreatment Follow-Up Visits; one 4 weeks after the last dose of study drug (Visit 19) and a second 12 weeks after the last dose of study drug (Visit 20). If clinically indicated, more frequent safety assessments can be conducted as part of unscheduled visits during the posttreatment Follow-Up period.

Number of Subjects

- Stage A: Approximately 250 MCI/Prodromal or mild to moderate AD subjects will be screened to provide 60 randomized subjects (target of 15 subjects per treatment arm). There will be no limit to the number of subjects randomized from either clinical cohort. (revised per Amendment 01)
- Stage B: Up to approximately 2100 MCI/Prodromal subjects will be screened to provide up to 500 randomized subjects. The final number of MCI/Prodromal subjects will depend upon whether the prespecified criteria for either early success or futility are met. In addition, up to approximately 835 subjects with mild to moderate AD will be screened to provide up to 200 randomized mild to moderate AD subjects. The final number of mild to moderate AD subjects randomized in Stage B will depend upon the number of mild to moderate AD subjects previously randomized during Stage A. (revised per Amendment 01)

Inclusion Criteria

1. Meets the core clinical research criteria of the NIA-AA for MCI due to AD or AD dementia and is "staged" or classified as either MCI or mild to moderate dementia and also complies with the following: (revised per Amendment 01)

Required at both Screening and Baseline:

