In Stage A, all subjects will be randomized to receive either placebo or E2609 at 5 mg, 15 mg, or 50 mg QD. In Stage B, subjects in the MCI/Prodromal cohort will continue to be randomized to receive either placebo or E2609 at 5 mg, 15 mg, or 50 mg QD. In Stage B, subjects in the Mild to Moderate AD cohort will be randomized to receive either placebo or E2609 at 15 mg or 50 mg QD, but not the 5-mg QD dose. The rationale for not including an E2609 5-mg QD dose in the dose regimens for Stage B subjects with mild to moderate AD is

that more advanced disease may require greater reduction in CSF A β levels for comparable effects. (revised per Amendment 01)

After 60 subjects in Stage A have completed 4 weeks of treatment, an interim analysis of the E2609 PK and PD profiles will be used to confirm the E2609 doses to be used for Stage B, where PD is measured as reductions from baseline in CSF A β (1-x) levels. (revised per Amendment 01) If the 95% confidence interval of the mean percentage change from baseline in CSF A β (1-x) measured after 4 weeks of treatment with a dose of E2609 does not include its intended target value (ie, 25%, 50%, and 75% reductions from baseline, respectively for E2609 at 5 mg, 15 mg, and 50 mg), PK/PD modeling will be conducted. This PK/PD modeling will use the observed PK and PD data from Stage A and will relate the average steady state plasma concentration of E2609 to steady state CSF A β (1-x) percentage reduction from baseline after 4 weeks of dosing. From this model, the new target plasma steady state concentrations of E2609 required to achieve the target levels of CSF A β (1-x) reduction will be estimated again. Dose adjustment for Stage B may be considered if it is possible to get closer to the new target plasma steady state concentrations of E2609 required to achieve the intended target levels of CSF A β (1-x) reduction than is possible with the initially planned doses, given the limitation that E2609 dose adjustments will have to be in 5-mg increments or decrements. Subjects already randomized to a dose that needs to be adjusted will be switched to the new adjusted dose and complete their treatment at this new dose.

If dose adjustment is required for Stage B, a protocol amendment reflecting the new doses will be submitted.

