9.7.1.8 Safety Analyses

Evaluations of safety will be performed on the Safety Analysis Set. The incidence of AEs (including changes from baseline in physical and neurological examinations, and dermatological assessments), out-of-normal-range laboratory safety test variables, abnormal ECG findings, out-of-range vital signs, suicidality (C-SSRS), and results of the sleep questionnaire, along with the change from baseline in laboratory safety test variables, ECGs, safety MRI, and vital sign measurements will be summarized by treatment group using descriptive statistics.

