9.7.4 Other Statistical/Analytical Issues

Adaptive Randomization in the MCI/Prodromal Cohort

Randomization to placebo or 1 of 3 dose groups of E2609 will be fixed for the first 100 MCI/Prodromal subjects randomized in the study (1:1:1:1; placebo to each of the 3 active doses for the first 100 MCI/Prodromal subjects randomized, including those randomized from both Stage A and Stage B). Thereafter, randomization probabilities to each treatment group will be updated at each interim analysis, such that the randomization probability will be increased for the placebo group and dosage groups that represent the potential target dose (ED_{90}), and simultaneously decreased for other active arms. (revised per Amendment 01)

Randomization in the Mild to Moderate AD Cohort (revised per Amendment 01)

In Stage A, the mild to moderate AD subjects will be randomized to placebo or 1 of 3 E2609 dose groups (5 mg, 15 mg, and 50 mg of E2609) at a 1:1:1:1 ratio, while in Stage B, the mild to moderate AD subjects will be randomized to placebo or 1 of 2 E2609 dose groups (15 mg and 50 mg E2609) at a 1:1:1 ratio. (revised per Amendment 01)

Stratification (revised per Amendment 01)

Within the 2 clinical cohorts (MCI/Prodromal and mild to moderate AD), subjects will be stratified at randomization by *ApoE4* status (positive or negative) and prior treatment with AChEIs or memantine or both (yes or no). (revised per Amendment 01)

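### Laboratory, lymphocyte, immunoglobulin, vital-sign and ECG displays are specified by dose only, although the mix of MCI/Prodromal and AD subjects differs by dose and is not controlled

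*Protocol*

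**What the plan says.** **Allocation.** Section 9.7.4 randomizes the cohorts separately. In Stage A, AD subjects have four arms, placebo and "1 of 3 E2609 dose groups (5 mg, 15 mg, and 50 mg of E2609) at a 1:1:1:1 ratio". The Stage B rule drops the 5 mg arm and allocates equally to three arms: "the mild to moderate AD subjects will be randomized to placebo or 1 of 2 E2609 dose groups (15 mg and 50 mg E2609"). Section 9.4.4 gives the Stage B AD arms as placebo or "E2609 at 15 mg or 50 mg QD, but not the 5-mg QD dose". MCI/Prodromal subjects are allocated 1:1:1:1 for the first 100 and response-adaptively after that, with probability shifted towards placebo and the likely target dose.

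**Safety displays.** The general rule in Section 9.7.1.8 is that results "will be summarized by treatment group using descriptive statistics". For adverse events, Section 9.7.1.8.2 says "The TEAEs will be summarized by treatment group on the Safety Analysis Set" and then adds subgroup summaries, one of which is clinical population (MCI/Prodromal or mild to moderate AD). Sections 9.7.1.8.3 to 9.7.1.8.5 contain no such addition. Laboratory values, vital signs and ECGs are given by visit and treatment group. Lymphocyte subsets and immunoglobulins follow the laboratory rule, and for the lymphocyte plots: "Mean lymphocyte subsets and the mean change from baseline in lymphocyte subsets will also be displayed graphically over time by dose".

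**Status of the question.** Section 8.1 makes safety, with immunological and hematological parameters named, a primary objective in both cohorts. Section 9.2.3 justifies separate analysis of the cohorts by the risk that AD data would confound the MCI/Prodromal results.

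**The concern.** Treatment is randomized within cohort, and the two cohorts use different ratios that change over time. A dose group formed by putting the cohorts together therefore has a cohort mix set by the allocation rules and by recruitment. It is not the same across doses, and a comparison of such groups is not a randomized comparison.

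The displays affected are the ones that matter most for this compound. Section 7.1 reports lymphocyte reductions at 200 and 400 mg in the multiple-dose study, with some CD4 reduction at 50 to 100 mg. The plot of lymphocyte change by dose is where a reader will look for a dose-response over 18 months. If the cohorts differ in trend or in drop-out, part of an apparent dose-response could be cohort mix, or a real one could be masked.

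**Working it through.** **Inputs**
- Stage A: "60 randomized subjects (target of 15 subjects per treatment arm"), both cohorts together (Synopsis, Number of Subjects). The cohort split within the 60 is not fixed, so the number of AD subjects in Stage A, *a*, is taken from 0 to 60.
- Maximum 500 MCI/Prodromal and 200 AD subjects, Stage A included (Section 9.3).
- AD ratios 1:1:1:1 in Stage A and 1:1:1 without 5 mg in Stage B; MCI fixed for the first 100, that is 25 per arm (Section 9.7.4).
- Final MCI arm sizes are not fixed by the protocol. They are assumed below and varied.

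**The plan's own figure.** 60/4 = 15 per arm in Stage A, as stated. Since AD subjects get 5 mg only there, at most about 15 can be assigned it.

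**AD subjects per arm**
- 5 mg: *a*/4, which is 0 (*a* = 0), 7.5 (*a* = 30) or 15 (*a* = 60).
- Placebo, 15 mg and 50 mg, each: *a*/4 + (200 − *a*)/3, which is 66.7, 64.2 or 61.7.

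**AD share of a dose group** = AD / (AD + MCI in that arm). With 125 MCI per arm and *a* = 60, 5 mg is 15/140 = 10.7% and each other arm is 61.7/186.7 = 33.0%.

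| MCI allocation (assumed) | *a* | AD share, 5 mg | AD share, other arms |
|---|---|---|---|
| 125 in each arm | 0 | 0% | 34.8% |
| 125 in each arm | 30 | 5.7% | 33.9% |
| 125 in each arm | 60 | 10.7% | 33.0% |
| 5 mg stays at 25, other 475 split equally | 0 | 0% | 29.6% |
| 5 mg stays at 25, other 475 split equally | 30 | 23.1% | 28.8% |
| 5 mg stays at 25, other 475 split equally | 60 | 37.5% | 28.0% |
| Placebo and 5 mg favoured (225/225/25/25) | 0 to 60 | 0 to 6% | placebo 22 to 23%; 15 and 50 mg 71 to 73% |
| MCI stops at 200, 50 in each arm | 0 to 60 | 0 to 23% | 55 to 57% |

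**Effect on a pooled contrast.** Let D be the AD minus MCI difference in the outcome, the same in every arm, with no drug effect. The pooled mean in arm *j* is the MCI mean plus *p*(*j*) × D, where *p*(*j*) is the AD share. The spurious 50 mg minus 5 mg difference is [*p*(50) − *p*(5)] × D:
- Equal allocation: 0.348D (*a* = 0), 0.283D (*a* = 30), 0.223D (*a* = 60). Placebo, 15 mg and 50 mg share the same mix here, so contrasts among them are not distorted.
- 5 mg held at 25 MCI, *a* = 60: 0.280 − 0.375 = −0.095, so the sign reverses.
- Placebo and 5 mg favoured, *a* = 0: the 50 mg versus placebo contrast is also affected, by (0.727 − 0.229)D = 0.50D.

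**The case against.** **Pooling is inferred.** The protocol never says outright that these displays combine the cohorts. The Full Analysis Set is also defined without reference to cohort, and the primary analysis still restricts it to MCI/Prodromal subjects. Section 9.1 gives each cohort its own placebo group in Stage B, and Section 9.2.3 speaks of independent analysis for decision making. The SAP could add the split. This stands as a caution. But the protocol states the clinical-population split for adverse events and not for the neighbouring displays, so the plain reading of by treatment group, or by dose, is a combined display.

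**No cohort effect is documented.** Both cohorts share the 50 to 85 age range and most eligibility criteria. Appendix 5 attributes low lymphocyte counts to age and not to disease, and no cohort difference in age is given. Change from baseline removes differences in level. This stands: D is unknown. What change from baseline does not remove is a difference in trend or in drop-out.

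**The consequences are limited.** The summaries are descriptive, no dose-selection rule hangs on them, discontinuation uses individual counts (Section 9.3.3), and an unblinded safety board reviews the data. Section 9.7.1.4 tabulates clinical population by treatment group, so an imbalance would be visible. All true, but seeing the imbalance does not separate cohort from dose in a plot.

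**Stronger readings that the documents do not support.** A reader might infer that all safety tables are affected; adverse events are not, because Section 9.7.1.8.2 already splits them. A reader might also infer that the 5 mg group is bound to be nearly all MCI/Prodromal and the others about one third AD. That holds only for roughly equal MCI allocation and full enrolment.

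**Conclusion.** The point holds for laboratory values, lymphocyte subsets, immunoglobulins, vital signs and ECGs. As specified, their dose contrasts are not randomized comparisons, because cohort mix differs by dose and nothing in the plan controls it. At most about 15 AD subjects can receive 5 mg, against about 62 to 67 in each other arm. Under equal MCI allocation and full enrolment the AD share is 0 to 11% against 33 to 35%, and a cohort difference D would appear as 0.22D to 0.35D between 50 mg and 5 mg. Under other allocations the imbalance can be larger, involve placebo, or change direction.

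This rests on 200 AD subjects in total, Stage A included. Section 9.1 can also be read as up to 200 in addition to Stage A; the other arms would then be 35 to 40% AD with equal MCI allocation, and the 5 mg figures would not change. D is not in the documents, so no bias in any lymphocyte result is demonstrated. What is established is that the planned displays could not tell such a bias from a dose effect. Section references are to the Version 3.0 (Amendment 01) text; Appendix 5 comes from a later amendment whose Section 9.7 is not in the part available.

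**What to change.** In Sections 9.7.1.8.3 to 9.7.1.8.5, specify that laboratory, lymphocyte-subset, immunoglobulin, vital-sign and ECG displays, including the lymphocyte plots, are presented by treatment group within clinical population, as Section 9.7.1.8.2 already does for adverse events. Show the AD 5 mg group separately and label it as a Stage A group of at most about 15 subjects. If cohorts are also combined, base any dose comparison on differences from placebo taken within cohort and then averaged with stated weights. Because 5 mg is absent from the AD cohort in Stage B, say how that arm's AD stratum is weighted.

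The cost is additional tables and figures. No new data, visits or changes to randomization are needed, and cohort is already recorded because randomization is carried out within it.
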